3.2 Preliminary steps

For all study designs, preliminary steps for the cluster investigation are the following:

- Confirm the cluster/outbreak.
- Verify the diagnosis of A(H1N1)v infection.
- Case identification: all persons with respiratory symptoms should be identified within the cluster (retrospectively and prospectively, if appropriate). Swabs should be taken as soon as possible. For information on case definitions and laboratory methods, see the respective study design chapters. In a well-defined cluster, the entire population can be surveyed.
- Establishing a case line listing with basic information on the cases or a line listing the total population, if the cluster is small.
- Cases should be described in terms of time, place and person.
- A study design approach for an analytical study should be decided upon (see next section).

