3.4.8 Confounding factors and effect modifiers

To control for differences in vaccinated compared to non-vaccinated individuals, information on potential confounding factors is collected.

The minimum confounding factors to be considered include chronic diseases, indicators of the severity of chronic diseases, current vaccination with seasonal flu vaccination (if IVE of pandemic vaccine is calculated), current vaccination with pandemic flu vaccination (if IVE of seasonal vaccine is calculated), previous influenza vaccination, antiviral drug use, smoking and functional status (the latter if cluster is in elderly people).

Below is a list of confounding factors and effect modifiers. Not all information will be relevant or available, given the nature of the cluster.

The precise information collected in each study should be specified in annexes.

Chronic diseases

An individual will be classified as belonging to a high risk group if:

- medical records indicate presence of chronic disease (see Table 1);
- he/she reports having the following underlying conditions:
 - diabetes if treated for insulin-dependent or non-insulin-dependent diabetes;
 - cardiovascular disease if has had any of the following: myocardial infarction, angioplasty, coronary artery bypass surgery, stroke, transient ischaemic attacks, treated hypercholesterolaemia, treated hypertension;
 - chronic pulmonary disease;
 - immunodeficiency.

Table 1: ICD and ICHPPC-2 codes for chronic diseases

Chronic diseases	ICD Code	ICHPPC-2 code
Anaemia spleen	280–289 and 759.0	B82
Cirrhosis	571	D97
Diabetes and endocrine	250 and 251	T89 and T90
Heart disease	093, 112.81, 130.3, 391, 393–398, 402, 404, 410–429, 745, 746, 747.1, 747.49, 759.82, 785.2, and 785.3	K71, K74-77, K81-K84, K86-K87 and K99
Haematologic cancer	200–208	B72 andB74
Immunodeficiency and organ transplant	042, 079, 279, V08, and V42	B99
Lung disease	011, 460, 462, 465, 466, 480–511, 512.8, 513–517, 518.3, 518.8, 519.9, and 714.81	A70, R83, R79, R95, R96 and R99
Non-haematologic cancer	140–198 and 199.1	A79, D74-D78, F74, H75, K72, L71, N74, N76, R84, R85, S77, S79, T71, T73, U75-U77, U79, W72-W73, X75-X77, X81 and Y77-Y
Nutritional deficiencies	254, 255, 259.2, and 260–269	T05 and T99
Renal disease	274.1, 408, 580–591, 593.71–593.73, and 593.9	U99
Dementia, stroke	290-294, 331, 340, 341, 348, and 438	P70 and K90
Rheumatologic diseases	446, 710, 714.0–714.4, 714.8, 714.89, and 714.9	L88

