☐ The precise codes used in each study should be specified in study annexes.

Severity

The severity of the underlying conditions will be measured by the number of hospital admissions due to the underlying conditions in the year prior to study inclusion.

Smoking history

Smoking history will be collected and coded as 'never smoked', 'former smoker' (stopped smoking at least one year before inclusion in the study) and 'current smoker'.

Former vaccination

Former vaccination includes:

 Vaccination against influenza in the previous two years (collecting information on vaccination for each of the seasons).

Functional status (where applicable)

Information on functional status will be collected in terms of needing assistance with bathing.

Antiviral administration

Use of antivirals will be documented: type, dose and date of administration.

Other confounding factors that should be considered if available or relevant include:

- Level of social interaction
 - Number of household members
 - Children: nursery vs. school-age children
- Indicators of socio-economic status
 - Education level
 - Profession
 - Others (e.g. deprivation score by area of residence)
- Any other available and relevant for the study population

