3.5.5 Controls

The selection of controls varies according to the nature of the cluster.

Controls must be representative of the source population from which the cases arise in respect to vaccination coverage. In a traditional case-control study, controls who are still disease free (i.e. who did not have A(H1N1)v infection or other outcome of interest) are chosen at the end of the cluster/outbreak. In a case-cohort study, controls are selected from persons who are disease-free at the beginning of the cluster/outbreak. Therefore, persons who got the outcome of interest during the cluster/outbreak can be included as controls. Control selection among people still free of the outcome of interest when a case arises forms a density case-control study.

Controls can be unmatched or matched to cases.

Selection and characteristics of controls should be listed in study annexes.

Control inclusion criteria

Controls are eligible if they meet the above control definition and accept to participate.

☑ Oral or written informed consent according to country procedures should be specified in the study annexes.

Control exclusion criteria

Controls are excluded if they are not eligible for influenza vaccination because of having a condition listed in the summary of products characteristics (e.g. anaphylactic hypersensitivity to eggs or its components) or if they refuse participation. People with laboratory-confirmed diagnosis of A(H1N1)v infection since the beginning of the pandemic (or other date, according to the duration of the pandemic) and prior to the beginning of the outbreak/cluster of influenza are excluded, as they are not at risk.

People who were not swabbed but had respiratory symptoms in the interval from the beginning of the pandemic (or other date, according to the duration of the pandemic) and prior to the beginning of the outbreak/cluster will be documented and analyses carried out including and excluding them.

Reasons for exclusion must be documented.

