4.4 Misclassification bias

Notification of a cluster is often not prompt. This can lead to a delay between onset of illness and laboratory confirmation, which can result in misclassification of cases. If the swabbing delay is associated with vaccination status, then the IVE can be over- or underestimated. If this misclassification is irrespective of vaccination status, it can, under certain conditions, reduce test power lead bias study estimators to the null value.

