vacc_05	Numeric (categorical)	0 = No 1 = Yes 8 = Don't know	Previous influenza vaccination 2005–6
vacc_04	Numeric (categorical)	0 = No 1 = Yes 8 = Don't know	Previous influenza vaccination 2004–5
Diabetes	Numeric (categorical)	0 = No 1 = Yes 8 = Don't know	Diabetes and endocrine
heart_dis	Numeric (categorical)	0 = No 1 = Yes 8 = Don't know	Heart disease
immune	Numeric (categorical)	0 = No 1 = Yes 8 = Don't know	Immunodeficiency and organ transplant
Lungdis	Numeric (categorical)	0 = No 1 = Yes 8 = Don't know	Lung disease
Severity	Numeric (count)	integer	Number of hospitalisations in the previous year for the chronic disease
fs_bath	Numeric (categorical)	0 = No 1 = Yes 8 = Don't know	Requires assistance to bath
Pregnant	Numeric (categorical)	0 = No 1 = Yes 8 = Don't know	Pregnancy status
Smoking		0 = Never 1 = Former 2 = Current 9 = Don't know	Never, former (stopped smoking at least one year before inclusion in the study), current smoker
Antivir	Numeric (categorical)	0 = No 1 = Yes 8 = Don't know	Recent use of antivirals
Antivirdate	Date	dd/mm/yyyy	Date of antiviral administration
Antivirdose	Text		Doses of antiviral taken
Antivirbrand	Text		Type of antiviral taken (brand name)
ili_prior	Numeric (categorical)	0 = No 1 = Yes 8 = Don't know	ILI since beginning of pandemic, but prior to cluster
Ili_prior_lab	Numeric (categorical)	0 = Negative 1 = Positive 2 = Not done 8 = Don't know	Laboratory result (positive/negative)
ili_prior_virus	Text		Laboratory result: virus type and subtype of recent ILI
contra	Numeric (categorical)	0 = No 1 = Yes 8 = Don't know	Exclusion criteria: contraindication for influenza vaccination

This table represents a selection of covariates. Variables can be included or excluded as necessary.

Other annexes containing details of specific studies should be added to the current protocol.

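### The look-back year for chronic-disease severity ends at study inclusion, not at the start of the cluster, so influenza-triggered admissions can enter a baseline confounder and shift adjusted VE in either direction

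*Protocol*

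**What the plan says.** Section 3.4.8, under Severity, uses the "number of hospital admissions due to the underlying conditions in the year prior to study inclusion". Section 3.5.8 (Confounding factors/effect modifiers) repeats this for the case-control designs. The Annex defines the variable Severity as "Number of hospitalisations in the previous year for the chronic disease", with no start or end date.

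Severity belongs to the core adjustment set: "The minimum confounding factors to be considered include chronic diseases, indicators of the severity of chronic diseases", with functional status added for clusters in elderly people. On functional status, section 3.4.8 says "Information on functional status will be collected in terms of needing assistance with bathing", and the Annex item fs_bath reads "Requires assistance to bath". Neither gives a reference date.

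The protocol never dates study inclusion, but three statements bear on it:
- Section 3.2: "all persons with respiratory symptoms should be identified within the cluster (retrospectively and prospectively, if appropriate".
- Section 3.5.5: traditional controls "are chosen at the end of the cluster/outbreak".
- Section 4.4: "Notification of a cluster is often not prompt".

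**The concern.** A baseline confounder should be fixed before the outcome can influence it. Here the window closes at inclusion, which may come after the person has been ill. If influenza worsens someone's lung or heart disease and the admission is recorded under that disease, it counts as prior severity. Cases then look more severely ill at baseline than they were, and non-cases do not. Stratifying on such a variable, or adjusting for it, no longer recovers the estimate that true pre-outbreak severity would give.

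Elsewhere the protocol does date such items. Section 3.4.2 counts prior infection only up to the start of the outbreak, ili_prior is limited to the time before the cluster, and Hosp refers to the current outbreak. Severity and fs_bath have no such limit. Because this is a core protocol for many teams, the wording would be carried into each study that keeps it.

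**Working it through.** The plan states no figure on this point, so there is none to reproduce. The question is how far adjusted VE moves when severity is contaminated. All inputs below are assumptions unless a section is named.

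**Method.** Expected cell counts and the Mantel-Haenszel risk ratio over severity strata: RR = Σ(a·n0/N) / Σ(b·n1/N). Here a and n1 are vaccinated cases and vaccinated total, b and n0 the same for the unvaccinated, and N the stratum total. VE = 1 − RR.

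**Illustration A: true VE 0%, 1,000 people.** 20% have a genuine prior-year admission, their infection risk is 1.3-fold, and the attack rate in the rest is 20%. Coverage is 70% with a prior admission and 50% without (the section 4.2 pattern). 10% of infections trigger an admission booked to the chronic disease.

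- Prior admission: 140 vaccinated (36.4 cases), 60 unvaccinated (15.6 cases).
- No prior admission: 400 vaccinated (80 cases), 400 unvaccinated (80 cases).
- Adjusting for correctly dated severity: (36.4×60/200 + 80×400/800) / (15.6×140/200 + 80×400/800) = 50.92/50.92 = 1, so VE 0%.
- As written, 8 triggered cases per arm move into the severe stratum. It becomes 148 vaccinated (44.4 cases) and 68 unvaccinated (23.6 cases), leaving 392 per arm with 72 cases each. RR = (44.4×68/216 + 72×392/784) / (23.6×148/216 + 72×392/784) = 49.98/52.17 = 0.958, so VE 4.2%.

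**Reverse the confounding** (the section 4.3 pattern): coverage 35% with a prior admission and 60% without. The severe stratum becomes 79.6 vaccinated (27.8 cases) and 136.4 unvaccinated (40.2 cases); the other is 470.4 (86.4 cases) and 313.6 (57.6 cases). RR = (27.8×136.4/216 + 86.4×313.6/784) / (40.2×79.6/216 + 57.6×470.4/784) = 52.12/49.37 = 1.056, so VE −5.6%.

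**Restrict who can have such an admission.** With coverage 70/50%, suppose only 25% of those without a prior admission have a chronic disease at all. Then 2 cases per arm move, not 8. RR = (38.4×62/204 + 78×398/796) / (17.6×142/204 + 78×398/796) = 50.67/51.25 = 0.989, so VE 1.1%.

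**Ranges at true VE 0%** (attack rate in the rest 20–40%; triggered admissions 10–20% unless stated):

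| Scenario | VE, RR scale | VE, OR scale |
|---|---|---|
| Coverage 70/50%, equal admission risk | 2.6 to 7.7% | 4.5 to 10.0% |
| Same, admission risk 20% unvaccinated, 10% vaccinated | 1.6 to 4.7% | 2.9 to 6.1% |
| Same as first row, 2% triggered | 0.6 to 0.9% | 1.0 to 1.2% |
| Same as first row, 25% of the rest chronically ill | 0.7 to 2.2% | 1.3 to 2.8% |
| Equal coverage, equal admission risk | 0 | 0 |
| Coverage 35/60%, equal admission risk | about −3 to −11% | about −6 to −14% |

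**Illustration B: true VE 50%.** RR 0.5 with attack rates of 20% and 40% in the unvaccinated lies within the rows of Table 3 in section 3.4.9. Assumed: 20% with a prior admission; risk ratio 2 for them (1 where there is no confounding); coverage 70/45%, 50/50% or 35/60%; admission risk equal or halved in the vaccinated; severity coded as yes/no or as a count. Correctly dated severity returns 50% on the RR scale in every scenario. Severity as written gives:

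- 2% of infections triggering such an admission: 49.2 to 50.4%
- 10%: 46.1 to 51.9%
- 30%: 37.6 to 54.4%

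By pattern, over 2–30% triggered: 47.2 to 54.4% with confounding by indication, 46.4 to 50.0% with none, 37.6 to 49.5% with healthy vaccinees.

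**Hospitalisation outcome, worst case.** If every outcome admission is also counted as severity, a true VE of 50% becomes −26% to 75%, and a true 75% becomes 24% to 88%.

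**The case against.** Several stronger readings are tempting, and the document does not support them.

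- **That admissions for influenza itself are counted as severity.** The text counts only admissions due to the underlying conditions, and outbreak admissions for respiratory infection have their own variable, Hosp. Only influenza-triggered admissions attributed to the chronic disease can leak in. Nothing prevents that, however.
- **That functional status is read at inclusion.** No date is given. The present tense of an Annex label is a data-dictionary entry, not questionnaire wording. The defect there is a missing date.
- **That the primary VE is inflated, or that protection is created for a useless vaccine.** That needs frailer people to be vaccinated more. Section 4.3 names the opposite pattern, which pushes VE down. With equal coverage and equal admission risk, a useless vaccine shows no shift.
- **That every adjusted analysis is affected.** The case-control model list in 3.5.11 names functional status but not severity, section 3.4.11 leaves the cohort model to study annexes, and the Annex lets teams add or drop variables. Where cases are found prospectively, inclusion can precede illness.

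The larger shifts also rest on letting any infected person have a chronic-disease admission. Limiting this to people with a chronic disease cuts them to roughly a third or less, though less so in care homes, where chronic disease would be more common.

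These objections limit scope and size. They do not remove the fault, because the window is a stated rule, no section caps it at the start of the cluster, and no instruction tells teams to replace it.

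**Conclusion.** The concern holds in a limited form. The severity window can include the outbreak and a case's own illness, so a minimum-set confounder can be partly a consequence of the outcome, and adjusted VE can be biased either way. For laboratory-confirmed infection the shift is typically from under 1 to a few percentage points. With true VE 50% it is at most about 4 points on the RR scale when 10% or fewer infections trigger such an admission, and about 12 points in the most extreme scenario at 30%. It could be far larger for hospitalisation, but only to the extent that the same admissions count as both outcome and covariate.

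The protocol gives no admission risk, coverage by severity or prevalence of prior admission, so these sizes are illustrations and not estimates of the bias in any particular study. A distortion of the primary estimate is possible, not demonstrated. The change is worth making because it removes the problem at almost no cost.

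**What to change.** - In 3.4.8 and in 3.5.8 (Confounding factors/effect modifiers), define severity over the 12 months ending the day before the start of the cluster or outbreak, with the same calendar window for cases, non-cases and controls. Change the Annex variable Severity to match.
- Apply the same end date to the previous-year counts of hospitalisations and GP visits in 3.4.10 and 3.5.10.
- Define functional status, and fs_bath in the Annex, as the need for help with bathing before the start of the cluster.

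These are changes to definitions and questionnaire wording, and no extra data are needed. The one drawback is a slightly greater recall burden, since respondents must report their state before the outbreak rather than on the day of interview.

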3.4.9 Sample size

In a cluster investigation that is of manageable size, all persons in the study population should be surveyed. Therefore, the sample size is limited to the study population. Prior to the beginning of the study, calculations to determine the power of the study for detecting a given measure of effect with the set study population size can be useful. Elements needed to calculate the power are: ratio of unexposed to exposed, risk of illness in the unvaccinated, the number of vaccinated people and estimated measure of effect to detect. The table below shows some examples of power of a study with given parameters. Note that the power is lower than 80% with some of the parameters below.

Table 2: Examples of power of a study with given parameters

Power	Alpha	Ratio of unexposed/ exposed	Attack rate among the non-exposed	Minimum risk ratio to detect		Number of unexposed
0.25	0.05	1	10%	0.6	200	200
0.40	0.05	1	10%	0.5	200	200
0.53	0.05	1	20%	0.6	200	200
0.76	0.05	1	20%	0.5	200	200
0.92	0.05	1	20%	0.4	200	200
0.27	0.05	1	20%	0.6	100	100
0.43	0.05	1	20%	0.5	100	100
0.44	0.05	1	30%	0.6	100	100
0.66	0.05	1	30%	0.5	100	100
0.85	0.05	1	30%	0.4	100	100
0.63	0.05	1	40%	0.6	100	100

Power	Alpha	Ratio of unexposed/exposed	Attack rate among the non-exposed	Minimum risk ratio to detect		Number of unexposed
0.84	0.05	1	40%	0.5	100	100
0.96	0.05	1	40%	0.4	100	100
0.32	0.05	1	40%	0.6	50	50
0.50	0.05	1	40%	0.5	50	50
0.45	0.05	1	50%	0.6	50	50
0.67	0.05	1	50%	0.5	50	50
0.85	0.05	1	50%	0.4	50	50

In a cluster situation where the study population is too large to survey everyone, the cohort study can be done with individuals included in the random or systematic sample. The minimum sample size should be estimated to have precise VE estimates.

☐ The sample size calculation for the study should be detailed in study annexes.

The following table illustrates the various possibilities regarding sample size needed in order to achieve an alpha error of 0.05, a power of 0.8 or 0.9, a detectable relative risk (RR) ranging from 0.3 to 0.7 and an attack rate among the non-exposed ranging from 10% to 30%.

The sample size should be respected for each population subgroup in which a sub- (stratified) analysis (e.g. effect modification) is planned.

Table 3: Sample size calculations

Power	Alpha	Ratio of unexposed/exposed	Attack rate among the non-exposed	Minimum risk ratio to detect		Number of unexposed
0.90	0.05	1	10%	0.6	1014	1014
0.80	0.05	1	10%	0.6	771	771
0.90	0.05	1	10%	0.5	621	621
0.80	0.05	1	10%	0.5	474	474
0.90	0.05	1	10%	0.4	411	411
0.80	0.05	1	10%	0.4	316	316
0.90	0.05	1	10%	0.3	287	287
0.80	0.05	1	10%	0.3	222	222
0.90	0.05	1	20%	0.6	464	464
0.80	0.05	1	20%	0.6	354	354
0.90	0.05	1	20%	0.5	286	286
0.80	0.05	1	20%	0.5	219	219
0.90	0.05	1	20%	0.4	190	190
0.80	0.05	1	20%	0.4	147	147
0.90	0.05	1	20%	0.3	134	134
0.80	0.05	1	20%	0.3	104	104
0.90	0.05	1	30%	0.6	281	281
0.80	0.05	1	30%	0.6	214	214
0.90	0.05	1	30%	0.5	174	174
0.80	0.05	1	30%	0.5	134	134
0.90	0.05	1	30%	0.4	117	117
0.80	0.05	1	30%	0.4	90	90

Power	Alpha	Ratio of unexposed/exposed	Attack rate among the non-exposed	Minimum risk ratio to detect		Number of unexposed
0.90	0.05	1	30%	0.3	82	82
0.80	0.05	1	30%	0.3	64	64
0.90	0.05	1	40%	0.6	189	189
0.80	0.05	1	40%	0.6	145	145
0.90	0.05	1	40%	0.5	119	119
0.80	0.05	1	40%	0.5	91	91
0.90	0.05	1	40%	0.4	80	80
0.80	0.05	1	40%	0.4	62	62
0.90	0.05	1	40%	0.3	57	57
0.80	0.05	1	40%	0.3	45	45

3.4.10 Data

Data collection

Data will be collected from all study participants using a standardised questionnaire. The procedures to collect data should be defined by each study coordinator (e.g. face-to-face, by telephone, postal questionnaire, web-based, etc.).

Double data entry is needed.

Details on data collection methods, data entry and data transmission should be specified in study annexes.

Information collected

(see Annex)

- Study participant demographics
- Signs, symptoms
- Severity: hospitalisation, pneumonia, death
- Date of onset of symptoms
- Date of swabbing
- Laboratory results
- Selected underlying chronic conditions (including diabetes, heart disease, chronic obstructing pulmonary disorder and immunodeficiencies);
- Number of hospitalisations in the previous year (if relevant)
- Number of GP visits in the previous year (if relevant)
- Smoking history
- Current influenza vaccination(s) including date of vaccination, type (seasonal, pandemic), doses and brand (if possible)
- Former influenza vaccination
- Functional status (if relevant)
- Pregnant: yes/no (if relevant)
- Use of antivirals, type, dose and date of administration
- Information on respiratory symptoms or laboratory-confirmed A(H1N1) influenza since the beginning of the pandemic in their country (or other date according to the duration of the pandemic) and prior to the cluster/outbreak

Data validation

If data are collected using paper questionnaires, a sample of paper questionnaires should be checked against the study database to validate data entry.

The specific validations procedures should be specified in study annexes.

Data cleaning

Summary and frequency tables and graphic displays of appropriate variables will be used to find illegal, implausible or missing values within the dataset. Checks for inconsistencies will be carried out (e.g. date of swabbing before date of onset of symptoms). These values will be checked against the questionnaires or queried

with the study participant. Any changes to the data will be documented and stored separately from the crude database. Any recoding of data (e.g. age from date of birth) will be documented.

3.4.11 Analysis

Analyses will be carried out separately for seasonal and pandemic IVE and for different vaccine brands.

Separate analyses will be carried out for the different primary and secondary outcomes.

Analyses will be carried out including and excluding persons with recent respiratory symptoms (prior to cluster) that were not lab-confirmed, where information is available.

An analysis will be carried out including only persons 'fully vaccinated' in the vaccinated group. A second analysis will include persons 'fully' and 'partially vaccinated' in the vaccinated group.

Descriptive and univariable analyses

Participation variables include:

- total number not eligible
- total number eligible
- total number included: vaccinated and unvaccinated; and
- total number of subjects that refused participation.

Study population baseline characteristics by influenza vaccination status

Baseline characteristics include:

- Age
- Gender
- Socio-economic status indicators
- Comorbidities
- Functional status (if relevant to cluster)
- Pregnancy status
- Previous vaccination (influenza)
- Antiviral use
- Smoking history

Baseline characteristics of vaccinated and unvaccinated participants will be described using proportions and mean/medians (depending on variable type). Missing data for each characteristic will be described, along with approaches on how the missing data were dealt with.

In order to test for differences between vaccinated and unvaccinated characteristics, Student's t test, Mann-Whitney test, chi-square test or Fisher's exact test will be used (depending on the nature and the sample size).

Table 4: Study population baseline characteristics by influenza vaccination status:

(to be completed/modified according to the variables collected)

Characteristics	Vaccinated (N =)	Unvaccinated (N =)
Demographic		
Age		
• Sex		
 Socio-economic status 		
Comorbidities		
Functional status (if relevant)		
Pregnancy status		
Previous flu vaccination		
Antiviral use		
Smoking history		

Crude VE estimates

The vaccine effectiveness will be computed as $VE = (1 - RR) \times 100$; exact 95% CI are computed around the estimate for each outcome.

Stratified analysis

Analysis should be stratified according to:

- age groups;
- presence or absence of high risk conditions;
- effect modifiers are assessed one by one comparing the RR across the strata of the baseline characteristic;
- confounding is assessed by comparing crude and adjusted RR for each baseline characteristic.

Multivariable analysis

A multivariable analysis is conducted to control for negative and positive confounding. Variables will be tested for multicollinearity.

The type of multivariable analysis depends on the nature (high or low incidence) of the cluster and the type of denominator used (persons or person-time). Regression methods could include Cox, Poisson or logistic regression.

The multivariable analysis type and model building strategy should be specified in study annexes.

Sensitivity analysis

In order to assess effects of a potential confounding factor not included in the analysis on VE estimates, a sensitivity analysis could be conducted.

Any sensitivity analysis carried out should be specified in study annexes.

